## 8.2. Recording and reporting adverse events

The study period is defined for each patient as the time period from signature of the informed consent form through to the final follow up visit (visit 3). All adverse events (as defined in Table 8) that occur during the defined study period will be identified, recorded in the eCRF, including the following information:

1. The severity grade (mild, moderate, severe) or (grade 1-4)
2. Its relationship to the drug(s) of interest (suspected/not suspected)
3. Its duration (start and end dates or if continuing at final exam)
4. Whether it constitutes a serious adverse event (SAE)

In addition, all reports of the following special scenarios will be considered an adverse event irrespective of whether a clinical event has occurred:

- Drug-drug or drug-food interaction
- Drug exposure during pregnancy
- Drug use during lactation or breast-feeding,
- Lack of effectiveness
- Overdose
- Drug abuse and misuse
- Drug maladministration or accidental exposure
- Dispensing errors / Medication errors
- Off-label use
- Withdrawal or rebound symptoms

This includes any SAEs likely to arise from the trial indication or progression of underlying/concomitant illness(es) (e.g. progression of cancer in oncology trials), unless specified in the protocol as study specific exemptions.

All serious adverse events (SAEs) will be reported by the Investigator to the Sponsor within 24 hours of the investigator learning that an SAE occurred.

All non-serious AEs will be reported by the Investigator to the Sponsor within 7 days of awareness that the non-serious AE occurred.

Any occurrences of a pregnancy in a patient (or a patients partner) during study participation will be collected. All pregnancies will be followed up to determine outcome, including spontaneous or voluntary termination, details of the birth, and the presence or absence of any birth defects, congenital abnormalities, or maternal and/or newborn complications

### **8.2.1. Follow-up reports**

AEs will be followed until resolution or until it is judged to be permanent, and an assessment will be made at each visit (or more frequently, if necessary) of any changes in severity, the suspected relationship to the drug of interest, the interventions required to treat it, and the outcome.

## 9. STATISTICAL ANALYSIS

### 9.1. General

Intention-to-treat and per-protocol analyses will be undertaken. For the Intention-to-treat analysis, all patients entered into the study will be included in the analysis. For the per-protocol analysis, all patients entered who complete the study as per protocol (defined as attending baseline and all follow-up visits irrespective) will be included.

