### *Mild to moderate disease severity (BODE/Ex $\leq 4$ points)*

**Controlled:** Patients are controlled if, at the time of evaluation, their COPD:

- Impact is low, i.e. all of the following criteria are satisfied:
  - Limited signs of dyspnea: mMRC 0–1
  - Minimal recent rescue medication (short-acting bronchodilator) usage:  $\leq 3$  times in the last week
  - Limited impact on daily physical activity:  $\geq 60$  minutes walked per day
  - Absence of sputum, or (if present) white sputum**OR**
  - CAT:  $\leq 10$ ,**AND**
  - CCQ:  $\leq 1$**AND**
- Clinically Stable in the last 3 months:
  - Absence of COPD exacerbations, AND
  - Any changes in CAT have been less than  $< 2$  points in magnitude, OR,
  - Any changes in CCQ  $< 0.4$

**Uncontrolled:** all others

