### **4.3. Outcomes**

#### **4.3.1. Primary outcomes**

The primary study outcome will be measured over the 21-month follow-up period.

The primary outcome of interest will be the difference in (annualized) rates of a composite endpoint (“Mortality, hospitalisations and serious COPD morbidity”) for patients controlled vs uncontrolled at baseline. The composite endpoint is defined as occurrence of any of the following:

- For COPD: unscheduled visits to the physician; emergency room attendance
- An exacerbation of COPD
- All-cause: hospitalization or mortality

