#### 4.1.3. Informed Consent

All patients will be asked to give written informed consent having had sufficient time to review and consider the patient information sheet. A signed and dated informed consent form will be obtained before screening procedures commence.

After informed consent is obtained, patients who are screened will be assigned a permanent identification number such that all patients from each investigational centre are given consecutive identification numbers following their inclusion.

A patient who is screened but not enrolled, e.g. because entry criteria were not met or enrolment did not occur within the specified time, may not be considered for screening again.

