#### 4.4.2. Visits 0–3: Baseline and follow-up assessment

In baseline visit (3 months after screening visit) patients will be included in one of the study groups (controlled patients or uncontrolled patients) according definitions. The following data will be collected at the time of each follow-up visit in order to assess disease stability between follow-up visits and disease control at time of each visit.

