#### 9.4. Missing data

The per-protocol will not account for missing data as missing data will be seen as a protocol violation and therefore a patient with missing data will be excluded from this population.

The Intent-to-Treat population (ITT) will have missing values imputed as follows:  
Any missing data will be assessed and attempts made to ensure that there are no underlying reasons for the data not being collected. i.e. that the data are missing at random.

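### The intention-to-treat set is fixed at Visit -1, but control status exists only from Visit 0, and the protocol gives two unreconciled routes for patients never classified

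*Protocol*

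**What the plan says.** **Analysis set.** Section 9.1 of the protocol: "For the Intention-to-treat analysis, all patients entered into the study will be included in the analysis". It sets no condition that Visit 0 was attended or that control status is known.

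**Point of entry.** The informed consent subsection (numbered 4.1.3) says "all patients from each investigational centre are given consecutive identification numbers following their inclusion". Inclusion is Visit -1.

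**Point of grouping.** Section 4.4.2: "In baseline visit (3 months after screening visit) patients will be included in one of the study groups (controlled patients or uncontrolled patients) according definitions". Section 4.3.1 states the primary outcome as a difference in rates "for patients controlled vs uncontrolled at baseline".

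**Residual rule.** Under both severity headings of the control definition, the second state is "Uncontrolled: all others". There is no unclassifiable state.

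**Missing data.** Section 9.4: "The Intent-to-Treat population (ITT) will have missing values imputed as follows". The text that follows says only that missingness will be assessed.

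**Outcome period.** Section 4.3.1 measures the primary outcome over 21 months of follow-up. Table 4 places inclusion at Visit -1, Visit 0 at 3 months and the last visit at 21 months.

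**The concern.** Entry and exposure are three months apart. A patient who dies, withdraws or misses Visit 0 is in the intention-to-treat set but has no measured exposure. The protocol then offers two answers: the residual rule makes the patient uncontrolled, or the value is imputed by a method the protocol does not give. The two can put the same patient in different groups.

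Both primary aims depend on this variable: the level of control in the cohort, and the outcome difference between controlled and uncontrolled patients. Early loss may also be related to the outcome. Section 8.1 lists hospitalisation among the exceptions under which a patient with an exacerbation may be discontinued, and hospitalisation, exacerbation and death are all components of the primary composite.

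The outcome clock adds to the problem. If the 21 months run from Visit -1, events in the first three months are counted as outcomes although they precede the grouping. An exacerbation in that window also makes the patient uncontrolled through the stability criterion, so one event can serve as both exposure and outcome.

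**Working it through.** **Inputs from Section 4.5.** 285 evaluable and 328 enrolled; 15% drop-out; 55% controlled; rate 1.2 per person-year, used here for the uncontrolled group as the planned contrast implies (the protocol gives it for a whole cohort); 0.72 in controlled patients. The plan's figures reproduce: 285 × 1.15 = 327.75, rounded to 328, and 0.72 / 1.2 = 0.60.

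**How many patients.** The protocol gives no figure for loss before Visit 0. Spreading the drop-out evenly over 21 months gives 328 × 0.15 × 3/21 = 7.0. A constant hazard gives 328 × (1 − 0.85^(3/21)) = 7.5. Both are about 2%. As an assumed range I take 2% to 15%; the upper end puts all planned drop-out before Visit 0.

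**Effect of defaulting them to uncontrolled.** Let m be the number without a status and u = 0.45 × (328 − m) the classified uncontrolled patients. If the m patients have rate r, and each patient has equal weight:

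rate in the uncontrolled group = (1.2u + rm) / (u + m); rate ratio = 0.72 / that rate.

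For 2%, m = 6.56 and u = 144.6:

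- Missingness unrelated to status, r = 0.55 × 0.72 + 0.45 × 1.2 = 0.936: rate 1.189, ratio 0.606.
- Counted with no events, r = 0: rate 1.148, ratio 0.627.
- Sicker, r = 2.4 (assumed): rate 1.252, ratio 0.575.

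The same calculation over the range:

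| Without status | Patients | Share of uncontrolled group | Truly controlled among them | Ratio, unrelated | Ratio, no events | Ratio, r = 2.4 |
|---|---|---|---|---|---|---|
| 2% | 6.6 | 4.3% | 3.6 | 0.606 | 0.627 | 0.575 |
| 5% | 16.4 | 10.5% | 9.0 | 0.614 | 0.670 | 0.543 |
| 10% | 32.8 | 19.8% | 18.0 | 0.627 | 0.748 | 0.501 |
| 15% | 49.2 | 28.2% | 27.1 | 0.640 | 0.835 | 0.468 |

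**No true difference.** If both groups truly have rate 1 and the unclassified patients have rate 2, the ratio is (u + m) / (u + 2m): 0.958, 0.905, 0.835 and 0.780 at 2%, 5%, 10% and 15%. The default alone then produces an apparent benefit of control.

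**Power.** I used a test on the log rate ratio with negative binomial variance, one year of follow-up, a 55:45 split, and dispersion 0.67 chosen so that 285 patients give 90%. With missingness unrelated to status, defaulting against restricting to classified patients gives 92.6% against 93.1% at 2%, and 84.9% against 89.4% at 15%.

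**Outcome clock.** 21 − 3 = 18 months follow Visit 0. The other 3 months of the stated period come before classification.

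**The case against.** **Patients never evaluated need not be uncontrolled.** Control is defined at the time of evaluation, and groups are formed at Visit 0, so the residual category can be read as covering evaluated patients only. Imputation is announced for the rest, and its method may be in an analysis plan that is not at hand. This stands in part: the residual rule is the literal reading but not the only one. What remains is that the protocol fixes the analysis set, the grouping and the residual rule itself, and does not say which route applies.

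**Some early losses are uncontrolled anyway.** A patient admitted for COPD before Visit 0 has had an exacerbation and fails the stability criterion under any rule. This stands. For that patient the problem is the outcome clock, not misclassification.

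**The per-protocol analysis avoids it.** That set is "defined as attending baseline and all follow-up visits irrespective", so patients without Visit 0 are out. It also removes everyone lost or dead later, although death is an endpoint component, so it is no substitute. Requiring a stable state at entry and excluding short life expectancy should keep early deaths few.

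**Stronger readings the documents do not support.** A reader might infer that any missing Visit 0 item, such as walking time or CCQ, makes a patient uncontrolled and so lowers the proportion controlled. It does not by itself: low impact can be met through the clinical criteria or the questionnaires, and the written definitions join the CAT and CCQ changes with OR (Table 3 uses AND). A reader might also infer a large, one-directional inflation by giving each lost patient one event in about 1.5 months, hence 8 per year, and averaging individual rates. The protocol supplies neither assumption. Even with those events, a pooled rate moves only from 1.20 to (259.2 + 7) / (216 + 0.875) = 1.23 (144 uncontrolled patients over 1.5 years, plus 7 over 0.125 year), and the planned Mann-Whitney test works on ranks.

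**Conclusion.** The conflict is real and modest in size. The intention-to-treat set is fixed at entry, the exposure three months later, and the protocol leaves two routes open for patients in between. The stated outcome period also allows events before classification to be counted.

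On the plan's own drop-out, spread evenly, about 7 of 328 patients are affected and the rate ratio of 0.60 moves to roughly 0.58 to 0.63. The direction is not fixed: sicker early losses exaggerate the contrast, while random losses or losses counted without events dilute it. At 10% to 15% unclassified the shift would matter, but the protocol does not suggest losses that large before Visit 0. These figures assume the planning rates, equal weight per patient, and values of r that are mine and not the protocol's.

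**What to change.** 1. In Section 9.1, define the primary comparison set as patients whose control status can be derived at Visit 0. A patient lost before Visit 0 has no later person-time and belongs in item 3, even if an exacerbation already settles the status.
2. In Section 4.3.1, count events and person-time from Visit 0, and reconcile the 21-month period with the 18 months that follow it.
3. Report patients lost between Visit -1 and Visit 0 with their number, reasons and events.
4. In the control definition, replace the residual rule: uncontrolled means that at least one required criterion was observed and not met. Where the observed items do not settle the status, code it as missing.
5. In Section 9.4, cover unsettled status with a best/worst-case sensitivity analysis: all controlled, then all uncontrolled.

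The cost is wording and a few patients fewer in the comparison, about 7 on the plan's drop-out figure. On the power model above, restricting to classified patients loses no power relative to defaulting the others to uncontrolled.

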### 9.2. Summary statistics

Summary statistics will be produced for both Phase 1 and Phase 2 of the study and for all baseline and outcome variables as a complete dataset and by treatment groups.

For variables measured on the interval or ratio scale, these will include:

- Sample size (n)
- Percentage non-missing
- Mean
- Variance / Standard Deviation
- Range (Minimum / Maximum)
- Median
- Inter-quartile Range (25th and 75th percentiles)

For categorical variables, the summary statistics will include:

- Sample size (n)
- Range (if applicable)
- Count and Percentage by category (distribution).

### 9.3. Statistical analysis

Baseline and outcome variables will be analysed as a complete dataset and by treatment groups (split by baseline COPD severity).

#### 9.3.1. *Baseline variables*

Baseline variables will include:

- Demographics and lifestyle:
  - Sex
  - Age

- Height, weight, BMI
- Occupation
- Impact:
  - Dysnea (mMRC score)
  - Sputum presence; sputum colour
  - Daily physical activity (minutes walked / day)
  - CAT
  - CCQ
  - Impact at time of assessment (High vs Low)
- Stability
  - Exacerbations in the last 3 months (patient-reported and based on clinical records)
  - Change in CAT and CCQ in the last 3 months (where available)
  - Stable (vs unstable) disease at time of assessment (Y/N)
- COPD Control Status:
  - Controlled
  - Poorly controlled
- Comorbidities
- COPD medications (and cost)
- Other concomitant medications (and cost)
- Lung function (FEV1, FVC, FEV1/FVC)
- BODE Index
- Smoking Status
  - History (pack years)
  - Current status

### **9.3.2. Outcome variables**

Outcome variables, captured at each follow-up visit will include:

- Impact:
  - Dysnea (mMRC score)
  - Sputum presence; sputum colour
  - Daily physical activity (minutes walked / day)
  - CAT (total score)
  - CCQ (total score)
  - Impact at time of assessment (High vs Low)
  - Change in impact since prior visit (Y/N)

- Change in impact from baseline (Y/N)
- Stability
  - Exacerbations in the last 3 months (patient-reported and based on clinical records)
  - Change in CAT and CCQ in the last 3 months (where available)
  - Stable (vs unstable) disease at time of assessment (Y/N)
  - Change in stability since prior visit (Y/N)
  - Change in stability from baseline (for visits 2-4; Y/N)
- COPD Control Status:
  - Controlled vs Poorly controlled
  - Change in control since prior visit
  - Change in control since baseline (for visits 2-4; Y/N)
- COPD medications (and cost)
- Mood (PhQ-4)
- Other concomitant medications (and cost)
- Lung function (FEV1, FVC, FEV1/FVC)
- Adverse events:
  - SAEs
  - AEs

### ***9.3.3. Analysis of primary and secondary outcomes***

Descriptive data are reported as means (standard deviations (SD)) or percentages, as appropriate. Comparisons between groups for descriptive summaries will be performed with the use of analysis of variance. The incidence of the composite endpoint (Mortality, hospitalisations and serious COPD morbidity) will be summarized as a per-person per-year rate.

Differences in the composite endpoint between groups (controlled and uncontrolled COPD patients) will be analyzed with the use of a nonparametric U-Mann Whitney test. In the initial exploration of data, composite endpoint will be analyzed as a qualitative variable (presence or not presence of death, hospitalisations or serious COPD morbidity) during year 1, with the use of logistic regression.

Multinomial logistic regression will be performed with the frequency of exacerbations during year 1 classified as none, one, or two or more to more fully characterize the associations between selected baseline factors and composite endpoint frequency.

Frequent exacerbations as two or more exacerbations in a year will be defined for the analysis.

A final multivariate logistic regression analysis will be used to calculate Odds ratios (OR) and their 95% confidence intervals (95%CI) for frequent exacerbations that will be included in the model as dependent variable. A previous analysis of potential confounding factors will be carried. The interaction was analyzed using the likelihood ratio test. Receiver operating characteristic (ROC) curves will be constructed derived from the final model to determine its capacity to predict endpoint. The Hosmer-Lemeshow goodness-of-fit test will be performed to assess the overall fit of the model (*Hosmer DW, Lemeshow S: Applied Logistic Regression, ed 1. New York, John Wiley and Sons Inc., 1989*).

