#### **4.5. SAMPLE SIZE CALCULATION**

Based on a previous pilot study in Spain, approximately 55% of patients with COPD are controlled based on the proposed criteria. The sample size has to be calculated in order to have enough sample of both subgroups (controlled/non controlled) in both levels of severity (mild to moderate and severe to very severe) that will allow to identify differences in outcomes (main outcome: difference in annualised rate of composite outcome). Since there is not previous information about the frequency of the composite outcome, we have performed a conservative approach using the expected frequency of exacerbations in the sample calculation. According to results from ECLIPSE Study, annualised rate of exacerbations in COPD patients in entire sample was 1.2 per person (15). We hypothesize that, in controlled COPD patients, this annual rate can be 40% lower (0.72 per person). Accepting an alpha risk of 5% and a beta risk of 10% in a two-sided test, a total of 285 COPD patients will be necessary to find this annualised incidence ratio difference as statistically significant. It is expected that two thirds of controlled patients have mild to moderate COPD and one third of these have severe to very severe COPD. With an expected drop-out rate of 15%, a total of 328 patients will be enrolled in the study. Sample size has been calculated with !NI2IS macro (SPSS V20).

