### 8.1. Definition of Adverse Events

All types of Adverse Events are defined in Table 8, below.

Worsening of the disease during the study will be recorded as an Adverse Event only if the presentation and/or outcome is more severe than would normally be expected from the normal course of the disease in a particular patient.

An exacerbation of COPD is defined as worsening COPD requiring the use of systemic corticosteroids, antibiotics and/or emergency room visit or hospitalisation.

An COPD exacerbation will not be considered an Adverse Event unless it meets the criteria for a serious adverse event. COPD exacerbations that do not meet the criteria for reporting as a serious adverse event will be documented separately from Adverse Events.

Patients with a COPD exacerbation will not be discontinued from the study unless hospitalisation is required, the patient meets any of the stopping criteria in Section 8, or the Principal Investigator believes it is in the patient's best interest to be withdrawn from the study.

Table 8. Definition of adverse events

Adverse Event (AE)	An untoward medical occurrence which does not necessarily have a causal relationship to the IMP or comparator, such as: 
 
 intercurrent illnesses
 
 physical injuries
 
 events possibly related to concomitant medication
 
 significant worsening (change in nature, severity, or frequency) of the disease under study or other pre-existing conditions. (Note: A condition recorded as pre-existing that is intermittently symptomatic [eg, headache] and which occurs during the study should be recorded as an adverse event.)
 

Adverse Drug Reaction (ADR)	An untoward and unintended response to an IMP which has a reasonable causal relationship to the IMP
Unexpected ADR	An ADR whose nature, severity, specificity, or outcome is not consistent with the term or description used in the local/regional product labeling (e.g. Package Insert or Summary of Product Characteristics) should be considered unexpected.

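### The primary composite rate is compared between non-randomised groups only by an unadjusted Mann-Whitney test, which gives no rate ratio, no confidence interval and no adjusted estimate.

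*Protocol*

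**What the plan says.** Protocol section 4.3.1 defines the primary outcome as the "difference in (annualized) rates of a composite endpoint" between patients controlled and uncontrolled at baseline. Section 4.4.2 forms the two groups by observation at Visit 0, three months after inclusion.

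Section 9.3.3 says the composite "will be summarized as a per-person per-year rate". It then names one test for the group comparison: "Differences in the composite endpoint between groups (controlled and uncontrolled COPD patients) will be analyzed with the use of a nonparametric U-Mann Whitney test". The regressions in the same section have other outcomes:

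- the composite as present or absent in year 1 (described as exploration, with no covariates named);
- exacerbations in year 1 as none, one, or two or more;
- frequent exacerbations: "A final multivariate logistic regression analysis will be used to calculate Odds ratios (OR) and their 95% confidence intervals (95%CI) for frequent exacerbations". The confounder step is attached to this last model.

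Section 9.3.4 uses confounders as covariates, but in an analysis of covariance of secondary outcomes.

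Section 4.5 sizes the study on a ratio of annual rates, 0.72 against 1.2 per person, with 55% of patients controlled: "Accepting an alpha risk of 5% and a beta risk of 10% in a two-sided test", 285 patients are required.

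**The concern.** The stated target is a difference in rates, the sample size rests on a rate ratio, and the analysis delivers a rank p-value. Three consequences follow.

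1. The main result would carry no rate ratio, and no rate difference with a confidence interval, so the hypothesised 40% reduction could not be compared with an interval estimate.
2. Control status is observed, not assigned. If severity or exacerbation history differs between the groups, the test cannot show how much of a difference belongs to control. For a study meant to validate a new concept, that is the question readers will ask.
3. Follow-up will be unequal, since 15% drop-out is expected. A rank test on individual annualised rates gives a short record the same weight as a full one. A rank test on raw counts would ignore follow-up time altogether.

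The protocol itself chooses the test, so a statistical analysis plan that follows it inherits the problem.

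**Working it through.** **1. Outcome against analysis**

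| Outcome | Planned analysis | Covariates |
|---|---|---|
| Composite annualised rate (primary) | Mann-Whitney | none |
| Composite yes/no, year 1 | logistic, exploratory | none named |
| Exacerbations 0 / 1 / 2+, year 1 | multinomial logistic | selected baseline factors, not named |
| Two or more exacerbations in a year | logistic | confounder step, none named |
| EQ5, CCQ, lung function, BODE | ANCOVA | baseline value, confounders |

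No row gives an adjusted estimate of the primary quantity.

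**2. The plan's own sample size**

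Inputs from section 4.5: λ0 = 1.2, λ1 = 0.72, ratio 0.60, p = 0.55 controlled, two-sided 5%, 90% power. With dispersion k and follow-up t in years,

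N = (1.960 + 1.282)² × [(1/(tλ0) + k)/(1 − p) + (1/(tλ1) + k)/p] / (ln 0.60)²,

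where (1.960 + 1.282)² = 10.507 and (ln 0.60)² = 0.2609.

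- t = 1, k = 0: bracket = 0.833/0.45 + 1.389/0.55 = 4.377, so N = 177.
- t = 1, k = 0.5 and 1: N = 258 and 339.
- t = 1.5, k = 0, 0.5 and 1: N = 118, 199 and 281.

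So 285 does not follow from the stated rates alone. It is reached at t = 1 with k of about 0.67. It is also nearly reached (288–291) by comparing one-year risks, 1 − exp(−1.2) = 69.9% and 1 − exp(−0.72) = 51.3%, as proportions. Because an unstated step can produce it, 285 is not called wrong here. With 18 months after classification (month 3 to month 21), it supports an unadjusted rate ratio at 90% power up to k of about 1.03.

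**3. Power of the two tests, N = 285, t = 1.5**

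For the rate model, SE = √(bracket/285) and power = Φ(0.511/SE − 1.96). Mann-Whitney power is simulated with gamma-Poisson counts and equal follow-up.

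| Assumed k | SE | Rate model | Mann-Whitney |
|---|---|---|---|
| 0.5 | 0.132 | 97% | 94% |
| 1 | 0.156 | 90% | 81% |
| 1.5 | 0.177 | 82% (up to 83% simulated) | 68–70% |

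The rate-model figures treat k as known, which flatters that model slightly.

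**4. Severity mix with no effect of control**

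Section 4.5 implies that one third of controlled patients are severe. Let s be the severe share of uncontrolled patients and r the rate ratio for severe disease, both assumed. Crude ratio = (2/3 + r/3) / ((1 − s) + s·r).

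| | s = 1/3 | s = 0.50 | s = 0.67 |
|---|---|---|---|
| r = 1.5 | 1.00 | 0.93 | 0.875 |
| r = 2 | 1.00 | 0.89 | 0.80 |

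A simulation of the unadjusted test under the null used N = 285, 18 months, k = 0.7 and 40% severe overall, with 65% of mild/moderate and 40% of severe patients controlled. The severe share is then 0.16/0.55 = 29% of controlled and 0.24/0.45 = 53% of uncontrolled patients. It rejected in 9%, 20% and 32% of runs at r = 1.5, 2 and 2.5, against 5% at r = 1.

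**5. The exacerbation-free criterion alone**

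Control requires three months without an exacerbation. Suppose the impact criteria carry no information, the mean rate is 1.2 and frailty is gamma with variance k. The relative rate of exacerbation-free patients is then E0 = 1/(1 + k × 1.2 × 0.25). With 55% controlled, the uncontrolled relative rate is (1 − 0.55·E0)/0.45.

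- k = 0.5: 0.870/1.159 = 0.75.
- k = 1: 0.769/1.282 = 0.60, equal to the whole hypothesised effect.

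**6. Follow-up weight**

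One event in one month is 12 per year; one event in 18 months is 1/1.5 = 0.67 per year. Ranked as individual rates, the two patients count equally.

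**The case against.** Several stronger readings are tempting and do not hold.

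- **That the protocol expects severity to be unbalanced.** It does not say so. "It is expected that two thirds of controlled patients have mild to moderate COPD" describes controlled patients only, and no mix is given for the others. The control thresholds also depend on severity, and are looser for severe disease on dyspnoea, CAT and CCQ, so imbalance cannot be presumed. The 0.80–0.93 range is conditional.
- **That exacerbation history is simply a confounder.** Absence of recent exacerbations is part of the definition of control. The 0.75 and 0.60 in step 5 show the classification predicting through its own component. That bears on what control adds beyond history. The hypothesis in section 2.1 is one of association, for which a crude comparison is a legitimate first estimand, though not a sufficient one.
- **That the rate difference is not estimated at all.** Per-person per-year rates will be summarised, so a crude difference can be read off. What is missing is a confidence interval and an adjusted estimate.
- **That one episode will be counted several times.** The composite lists "For COPD: unscheduled visits to the physician; emergency room attendance" beside exacerbation and hospitalisation, while section 8.1 defines an exacerbation as "worsening COPD requiring the use of systemic corticosteroids, antibiotics and/or emergency room visit or hospitalisation". The parts overlap, but section 4.3.1 can be read as one event per episode. This is a separate question about the endpoint definition and does not bear on the choice of test.

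It is also fair that section 9.3 promises a split by baseline severity and section 4.3.2 lists time to first composite event. Neither gives an adjusted primary estimate, and the outcome list in section 9.3.2 omits the composite. Section 9.3.3 does not say in so many words that individual annualised rates are ranked, so the weighting point is conditional on that. Finally, the power gap depends on dispersion: at k = 0.5 both tests exceed 90%, and at k = 1.5 both miss it.

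**Conclusion.** The point stands. The only test fixed for the primary composite rate is unadjusted and rank-based. It matches neither the outcome definition in section 4.3.1 nor the incidence ratio used for sizing in section 4.5, and adjustment is planned only for other outcomes. That much rests on the text alone.

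The size of the effect rests on assumptions. Severity imbalance alone could give a crude ratio of 0.80–0.93, or 1.00 if there is none. The power loss against a two-group rate model is about 3 percentage points at k = 0.5, 9 at k = 1 and 12–15 at k = 1.5. The protocol states no dispersion and no severity mix for uncontrolled patients. The rates are exacerbation rates standing in for the composite, and no power has been worked out for an adjusted model.

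**What to change.** In section 9.3.3, make the primary analysis a negative binomial regression of composite event counts from Visit 0 to month 21, with log person-time as offset. Counting should start at Visit 0 because the preceding three months help define the groups. Report two results, each with a 95% confidence interval:

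1. the unadjusted rate ratio, as the predictive association of control;
2. a prespecified adjusted rate ratio, read as the value of control beyond severity and history.

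Adjust for baseline severity, the number of exacerbations in the 12 months before Visit -1, age, smoking status and country. BODEx already contains exacerbations, so entering it together with the count would use that history twice. FEV1 % predicted and BMI with the exacerbation count avoid this, and also keep out dyspnoea, which is itself an impact criterion.

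Keep Mann-Whitney and the year-1 logistic model as supportive. Death ends follow-up and is not handled by a simple count model, so check its influence through the time-to-first-composite analysis already listed in section 4.3.2.

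The cost is a rewrite of the analysis section; the covariates are already collected at Visit -1 or known from the centre. The adjusted ratio may lie closer to 1 and be less precise. A rule on whether overlapping components of one episode count once would change section 4.3.1 and should be settled there separately.
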